1. SYNOPSIS

Name of Sponsor/Company: CytRx Corporation	
Protocol Number: INNO-206-P2-STS-01	Phase of Development: 2b
Title of the Protocol: A Multicenter, Randomized, Open-Label Phase 2b Study to Investigate the Preliminary Efficacy and Safety of INNO-206 (Doxorubicin-EMCH) Compared to Doxorubicin in Subjects with Metastatic, Locally Advanced, or Unresectable Soft Tissue Sarcoma	
Primary Objectives: The primary objective of this study is to determine the preliminary efficacy of administration of INNO-206 compared to doxorubicin in subjects with metastatic, locally advanced, or unresectable soft tissue sarcoma as measured by progression-free survival, progression-free survival at 4 and 6 months, tumor response and overall survival.	
Secondary Objectives: The secondary objective of this study is to evaluate the safety of INNO-206 compared to doxorubicin in this population assessed by the frequency and severity of adverse events (AEs), abnormal findings on physical examination, laboratory tests, vital signs, multiple-gated acquisition (MUGA) scans/cardiac ultrasound evaluations, electrocardiogram (ECG) results, and weight.	
Study Rationale and Significance: INNO-206 is a novel prodrug that binds covalently to albumin in the circulation. The drug is accumulated in tumors and doxorubicin is released in the tumor by cleaving the acid labile linker (EMCH) in the low pH tumor environment. This carrier-linked prodrug has demonstrated enhanced anti-tumor activity with reduced toxicity in several murine models when compared with free doxorubicin. Patients with metastatic, locally advanced, or unresectable soft tissue sarcomas have a poor prognosis with progression-free survival of around 4-5 months and median overall survival of approximately 15 months. Three-year survival rates as high as 30% have been observed in some clinical studies. Several chemotherapy regimens have been explored as palliative therapy for subjects with advanced soft tissue sarcomas. Combinations of ifosfamide and doxorubicin appear to offer the highest response rates and longest time to progression. However, these regimens are quite toxic and have not significantly increased survival in these individuals. INNO-206 may improve the activity of doxorubicin without increasing its toxicity as has been demonstrated in animal studies.	

Name of Sponsor/Company: CytRx Corporation	
Protocol Number: INNO-206-P2-STS-01	Phase of Development: 2b

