
Study Design and Methodology: This is a phase 2b open-label study evaluating the preliminary efficacy and safety of INNO-206 administered at 350 mg/m² (260 mg/m² doxorubicin equivalent) intravenously (IV) on Day 1 every 21 days for up to 6 consecutive cycles compared to doxorubicin administered at 75 mg/m² for up to 6 consecutive cycles. Subjects will be randomized 2:1 to receive either INNO-206 or doxorubicin.
 
Subjects will visit the study site every 21 days for their IV infusions, at which time safety monitoring, including AEs, a directed physical examination, laboratory evaluations (serum chemistry, complete blood count [CBC], and urinalysis), vital signs, weight measurements, ECOG performance status and ECGs will be performed. Cardiac function will also be followed periodically using either MUGA scans or cardiac ultrasounds. Treatment will continue every 21 days until tumor progression is observed, 6 cycles of treatment are completed or unacceptable toxicity occurs.
 
Tumor response will be monitored every 6 weeks from Cycle 1-Day 1 during treatment, at End of Treatment, 2 months following the End of Treatment scan (for those subjects completing 6 cycles), and then every 3 months until disease progression using the Response Evaluation Criteria in Solid Tumors (RECIST) 1.1 criteria. For those subjects that leave the study prior to completing Cycle 6, and who do not start another therapy, they can be followed 2 months following the End of Treatment scan, and then every 3 months until disease progression. However, if a subject receives another therapy, they should only be followed for overall survival [OS]. Progression-free survival [PFS], progression-free survival at 4 and 6 months and OS will be monitored as other primary objectives.
	

Name of Sponsor/Company: CytRx Corporation	
Protocol Number: INNO-206-P2-STS-01	Phase of Development: 2b

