
Name of Sponsor/Company: CytRx Corporation	
Protocol Number: INNO-206-P2-STS-01	Phase of Development: 2b

11. Current, serious, clinically significant cardiac arrhythmias, defined as the existence of an absolute arrhythmia or ventricular arrhythmias classified as Lown III, IV or V.
 
12. Baseline QTc >470 msec and/or previous history of QT prolongation while taking other medications. Concomitant use of medications associated with a high incidence of QT prolongation is not allowed
 
13. History or signs of active coronary artery disease with or without angina pectoris.
 
14. Serious myocardial dysfunction defined as scintigraphically (eg MUGA, myocardial scintigram) or ultrasound determined absolute left ventricular ejection fraction (LVEF) <45% of predicted.
 
15. History of HIV infection.
 
16. Active, clinically significant serious infection requiring treatment with antibiotics, anti-virals or anti-fungals.
 
17. Major surgery within 3 weeks prior to Randomization.
 
18. Substance abuse or any condition that might interfere with the subject's participation in the study or in the evaluation of the study results.
 
19. Any condition that is unstable and could jeopardize the subject's participation in the study.
	

Number of Subjects: One hundred and five (105) study subjects will be randomized 2:1 (INNO-206:doxorubicin) at approximately 30 study centers in the United States (US), Hungary, Romania, Ukraine, Russia, India, and Australia. Up to 32 subjects may be enrolled in India, with the remaining subjects distributed in the other locations.
	

Test Product, Dose and Mode of Administration: Lyophilized powder in vials that contain 200 mg of INNO-206 reconstituted by adding a solution of 50% ethanol: 50% sterile water, administration completed within 2 hours (of being reconstituted) as a 30 minute IV infusion in Lactated Ringer's solution. Total dose of 350 mg/m² (260 mg/m² doxorubicin equivalent).
	

Reference Therapy, Dose and Mode of Administration: Doxorubicin HCl Injection is a sterile parenteral, isotonic available in 5 mL (10 mg), 10 mL (20 mg), 25 mL (50 mg) single dose vials. Each mL contains doxorubicin HCl and the following inactive ingredients: NaCl (0.9%) and water for injection q.s. Hydrochloric acid is used to adjust the pH to a target of pH of 3.0. Prepare IV infusion per the package insert (see the Study Reference Manual).
	

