
Criteria for Evaluation:
 
Efficacy: The following efficacy variables will be evaluated as noted:
 
 • Progression-free survival • Overall survival • Objective tumor response (RECIST 1.1 criteria) • 4 and 6 month progression-free survival 
Safety: The following safety variables will be assessed over the duration of the study:
 
 • Adverse events • Ability to remain on assigned treatment (tolerability) • Clinical and laboratory data including physical examinations, vital signs, weight, MUGA/cardiac ultrasound evaluations, ECG results and laboratory test results • Use of concomitant medications 	

Name of Sponsor/Company: CytRx Corporation	
Protocol Number: INNO-206-P2-STS-01	Phase of Development: 2b

Statistical Methods: In accordance with the intention-to-treat principle, all randomized subjects who enter active treatment and have had at least 1 dose of study medication and 1 post-dose efficacy measurement will be included in the primary statistical analyses according to the treatment group to which they were originally assigned.
 
Efficacy: Tumor response will be monitored every 6 weeks from Cycle 1-Day1 during treatment, at End of Treatment, 2 months following the End of Treatment scan (for those subjects completing 6 cycles), then every 3 months until disease progression. For the estimation of progression-free and overall survival a Kaplan-Meier analysis will be performed. The percentage of subjects with complete or partial responses, or stable disease will be evaluated at 4 and 6 months.
 
Safety: The safety data will be summarized by treatment group. The treatment groups will be compared with respect to occurrence of each AE. Total number of AEs leading to withdrawal, and abnormal laboratory tests will be compared between groups using Fisher’s exact test. Adverse events, ability to remain on assigned treatment (tolerability), and abnormal findings on physical examinations, vital signs, weight, ECG results, laboratory test results, and use of concomitant medications, will be assessed to characterize the safety profile of the treatment regimens. Descriptive statistics denoting the changes from baseline to the final assessment visit with respect to key laboratory parameters and vital signs will also be provided.
	

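### The synopsis names objective tumor response as an efficacy variable, but its only stated response summary is CR or PR, or SD, status at 4 and 6 months, which is not an objective response rate

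*Combined protocol and SAP*

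**What the plan says.** All references are to the Amendment 2 synopsis and its Appendix A unless stated.

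- **Primary Objectives.** Efficacy is measured by PFS and by "progression-free survival at 4 and 6 months, tumor response and overall survival".
- **Study Design and Methodology.** Tumor response monitoring is described first. The text then says that PFS, "progression-free survival at 4 and 6 months and OS will be monitored as other primary objectives". Scans are every 6 weeks on treatment, at End of Treatment, 2 months after that scan, and then every 3 months until progression. A subject who starts another therapy is followed for survival only.
- **Criteria for Evaluation, Efficacy.** "Objective tumor response (RECIST 1.1 criteria)" and "4 and 6 month progression-free survival" are separate items.
- **Statistical Methods, Efficacy.** "For the estimation of progression-free and overall survival a Kaplan-Meier analysis will be performed". The only sentence on response is: "The percentage of subjects with complete or partial responses, or stable disease will be evaluated at 4 and 6 months".
- **Statistical Methods, population.** The primary analyses require "at least 1 dose of study medication and 1 post-dose efficacy measurement".
- **Number of Subjects.** "One hundred and five (105) study subjects will be randomized 2:1 (INNO-206:doxorubicin"), which is 70 and 35.

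The available text does not define an objective response rate or best overall response. It has no rule on confirmation or on subjects who cannot be evaluated, and no confidence interval or between-arm comparison for response. The synopses of the initial protocol and Amendment 1 have the same structure; the initial one uses 3 and 6 months.

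**The concern.** Objective response asks whether the tumor shrank enough to qualify as CR or PR at some point before progression. The stated summary asks which category a subject is in at month 4 and at month 6. Those are different questions, and the second is close to one that landmark PFS already answers.

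This matters here because the rationale is that the prodrug may be more active than doxorubicin, and tumor shrinkage is the most direct evidence of activity. The trial is also open-label. If the definition is left open, best response, confirmed response and landmark status all remain available once results are known.

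**Working it through.** The plan gives no response rate, response duration, alpha or power, so it has no figure of its own to reproduce. The check sets the sentence against the listed variable under each of its two readings. All rates and durations below are assumptions unless tied to the documents.

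**Reading 1: CR, PR and SD pooled.** A subject in any of these categories at month 4 is alive and unprogressed, which is the condition for 4-month PFS. The synopsis puts PFS at around 4-5 months. Treating that as a median *m* of an exponential distribution, S(t) = 0.5^(t/m):

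| | m = 4 | m = 5 |
|---|---|---|
| Month 4 | 50.0% | 57.4% |
| Month 6 | 35.4% | 43.5% |

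The pooled percentage would lie near these values whatever the share of responders. For example, 35 of 70 subjects unprogressed at month 4 gives 50% both with 14 responders plus 21 stable and with 0 responders plus 35 stable.

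The duplication is not exact. If 5-20% of subjects are lost by month 6 and counted as failures, the crude figure is S × (1 − loss). The 35.4% becomes 33.6% to 28.3%, and the 43.5% becomes 41.4% to 34.8%, a gap of about 2 to 9 points.

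**Reading 2: categories tabulated separately.** Appendix A places on-treatment scans at Cycles 3 and 5 (about weeks 6 and 12) and at End of Treatment (about week 18 after six 21-day cycles). With 30.4375 days per month, month 4 is day 121.75 (week 17.4) and month 6 is day 182.6 (week 26.1).

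Assume exponential response duration with median D = 3 or 6 months. The share lost by the landmark is 1 − 0.5^(elapsed/D), where elapsed is the time in months from first response to the landmark.

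| First seen | Landmark | Elapsed (months) | Lost, D = 6 | Lost, D = 3 |
|---|---|---|---|---|
| Week 6 (day 42) | Month 4 | 2.62 | 26% | 45% |
| Week 12 (day 84) | Month 4 | 1.24 | 13% | 25% |
| Week 6 | Month 6 | 4.62 | 41% | 66% |
| Week 12 | Month 6 | 3.24 | 31% | 53% |

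The range is 13-45% by month 4 and 31-66% by month 6. A response first seen at about week 18 falls just after month 4, so it cannot have been lost by then. A responder who starts another therapy before the landmark is no longer scanned, so the early response has no recorded status there.

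**What a defined response rate would deliver.** Exact (Clopper-Pearson) 95% intervals at an assumed 20% rate are 11.4-31.3% for 14/70 and 8.4-36.9% for 7/35. Approximate power for a two-sided 5% comparison of 35 with 70 subjects (normal approximation) is 23% for 10% vs 20%, 38% for 15% vs 30%, 54% for 20% vs 40%, and 65% for 10% vs 30%.

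**The case against.** The strongest reply is that the endpoint is present and only its detail is missing. Criteria for Evaluation lists objective response among the variables to be evaluated. The available text is synopsis and schedule only, and Appendix A points to a Section 7 that is not included, so a response definition may sit in the protocol body. This stands as a limit on scope. A reader might infer that the trial will never report an objective response rate, or that the sponsor chose to omit it. The documents do not support that.

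Two further inferences are also too strong. One is that the sentence certainly pools the three categories. Pooling is the natural reading, but the comma before stable disease also allows CR/PR and SD to be reported separately. The other is that the summary simply repeats landmark PFS. A crude percentage and a Kaplan-Meier estimate treat censoring and missing scans differently.

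It can also be said that the loss figures rest on assumed durations and that onset at the first scan gives the largest loss. Both are correct, which is why later onset is shown too.

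None of this supplies what is missing. Neither reading gives best overall response, so the one stated rule does not match the listed variable.

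**Conclusion.** The point holds for the synopsis and schedule: the only stated response summary does not estimate objective response. Pooled, it is close to 4- and 6-month PFS (about 50-57% and 35-44% under exponential PFS with a median of 4-5 months) and says nothing about the responder share. By category, it misses responses lost before the landmark: 13-45% by month 4 and 31-66% by month 6 among those first seen at week 6 or 12. Those ranges depend on an assumed exponential duration with median 3-6 months and are illustrations, not estimates for this trial.

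The mismatch should be corrected because it concerns a primary measure and a better rule is available from scans already scheduled. With 70 and 35 subjects, response would serve mainly for estimation.

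**What to change.** Replace the sentence in Statistical Methods, Efficacy with a definition along these lines: *Objective response rate is the percentage of subjects with a best overall response of CR or PR by RECIST 1.1 on any scan before progression or new therapy, reported per arm with an exact 95% confidence interval and with a confidence interval for the between-arm difference.*

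State also:

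- **Denominator.** If all randomized subjects are used, count those without an evaluable scan as non-responders. Say openly that this differs from the current primary population, which requires a dose and a post-dose efficacy measurement. That choice is a separate decision for the sponsor.
- **Confirmation.** Say whether a response must be confirmed.
- **Disease control.** Keep CR+PR+SD at 4 and 6 months as a separate summary under that label.

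If the protocol body already defines the response rate, align the synopsis with it. The cost is analysis wording only: no added scans, visits or subjects.

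### The Amendment 2 synopsis plans Fisher p-values for safety without a between-arm estimate or interval; at 70 versus 35 subjects, non-significance says little about less common toxicities

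*Combined protocol and SAP*

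**What the plan says.** All references are to the combined protocol and SAP, section 1 (Synopsis), in the Amendment 2 text.

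- **Objective.** Safety is the only secondary objective, and it is comparative: "The secondary objective of this study is to evaluate the safety of INNO-206 compared to doxorubicin in this population".
- **Rationale.** Study Rationale and Significance gives the hope behind the drug: "INNO-206 may improve the activity of doxorubicin without increasing its toxicity as has been demonstrated in animal studies".
- **Size.** Number of Subjects: "One hundred and five (105) study subjects will be randomized 2:1", with INNO-206 as the larger arm. No power, significance level or event rate accompanies this number.
- **Safety analysis.** Under Statistical Methods, Safety, the data are summarized by arm. Then: "The treatment groups will be compared with respect to occurrence of each AE", with no test named. The next sentence adds that the total of AEs causing withdrawal and "abnormal laboratory tests will be compared between groups using" Fisher's exact test. Other safety variables are to characterize the safety profile, with "Descriptive statistics denoting the changes from baseline to the final assessment visit" for key laboratory parameters and vital signs.

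The paragraph gives no risk difference or ratio, confidence interval, sidedness, margin, or rule for reading a non-significant result.

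**The concern.** Fisher's test asks whether the data are incompatible with equal rates. The comparative safety question is how much more, or less, toxicity INNO-206 carries than doxorubicin. When the test has little power, p>0.05 is expected whether or not toxicity has risen appreciably, so it cannot separate the two situations.

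What is at stake is how the secondary objective is reported. A table of arm percentages and p-values would not say what size of excess remains compatible with the data. A reader who has the rationale in mind could take a row of non-significant p-values as support for it.

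**Working it through.** **Inputs**

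- Arm sizes: 105 × 2/3 = 70 INNO-206 and 105 × 1/3 = 35 doxorubicin. The total and ratio are in the synopsis; the split is arithmetic.
- Test: Fisher's exact, as stated. Two-sided 5% is an assumption, since no level is given.
- Doxorubicin event rate p: not in the documents, so a range is used. The effect examined is a doubling, from p to 2p, also an assumption.
- Unit: subjects with at least one event.

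The plan has no safety power figure to reproduce.

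**Power of the stated test.** For all 71 × 36 possible outcomes (i events of 70, j events of 35), compute the Fisher p-value, then sum the probabilities of those with p ≤ 0.05:

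Power = Σ Bin(i; 70, 2p) × Bin(j; 35, p) × 1[Fisher p(i, j) ≤ 0.05]

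| Doxorubicin → INNO-206 | Power | Missed |
|---|---|---|
| 5% → 10% | 7.5% | 92.5% |
| 10% → 20% | 20.5% | 79.5% |
| 15% → 30% | 33.4% | 66.6% |
| 20% → 40% | 51.7% | 48.3% |
| 25% → 50% | 68.1% | 31.9% |
| 30% → 60% | 81.2% | 18.8% |
| 40% → 80% | 98.0% | 2.0% |

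Power passes 50% at a doxorubicin rate of about 19.5% and 80% at about 29.4%. With a one-sided 5% test it is 9.6%, 27.2%, 42.9% and 60.2% at 5%, 10%, 15% and 20%, so the picture for uncommon events is similar.

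**Size of the test.** With the same rate in both arms, the same sum gives an actual error rate of 2.7% to 3.9% for rates of 5% to 40%, against the nominal 5%.

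**What an interval would show.** The Newcombe interval combines the Wilson limits (l, u) of each arm. With d = p₁ − p₂ (INNO-206 minus doxorubicin):

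lower = d − √[(p₁ − l₁)² + (u₂ − p₂)²]; upper = d + √[(u₁ − p₁)² + (p₂ − l₂)²]

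Worked case, 14/70 (20.0%) versus 4/35 (11.4%): Wilson limits are 12.3% to 30.8% and 4.5% to 26.0%, and d = 8.6 points.

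- Lower: 8.6 − √(7.7² + 14.5²) = 8.6 − 16.4, about −7.9 (from unrounded limits).
- Upper: 8.6 + √(10.8² + 6.9²) = 8.6 + 12.8 = +21.4.

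| INNO-206 | Doxorubicin | Fisher p | Difference, points (95% CI) |
|---|---|---|---|
| 14/70 | 7/35 | 1.00 | 0 (−17.7 to +14.7) |
| 14/70 | 4/35 | 0.41 | +8.6 (−7.9 to +21.4) |
| 16/70 | 4/35 | 0.195 | +11.4 (−5.3 to +24.5) |
| 21/70 | 4/35 | 0.051 | +18.6 (+1.2 to +32.0) |

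Against 4/35, INNO-206 needs 22/70 (31%) before Fisher's p falls below 0.05. In the first row the observed rates are identical, yet an excess of nearly 15 points is not excluded (risk ratio interval 0.44 to 2.25). The p-value conveys none of this.

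**Does the interval detect more?** Only slightly. For the doublings from 10%, 15% and 20%, the Newcombe interval excludes zero in 21.9%, 36.9% and 54.6% of trials, against 20.5%, 33.4% and 51.7% for Fisher.

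**The case against.** **The low power comes from the sample size, not from Fisher's test.** This stands. The study is a phase 2b trial whose title calls its aims preliminary, and the interval detects little more. The case for change rests on what can be concluded, not on detection.

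**The plan provides more than a p-value.** Data are summarized by arm, so 20% against 11% would be visible. This stands in part. Arm percentages show the observed excess but not its uncertainty, and uncertainty decides whether a doubling is excluded.

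**The text may be incomplete.** Only synopses and schedules are supplied, and the schedule of evaluations refers to a Section 7 that is not among them. A fuller statistical section may specify intervals. If so, the synopsis only needs aligning with it.

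**Two stronger readings do not hold.** A reader might infer that the test misses most doublings. That is true only below a doxorubicin rate of about 19.5%; a rise from 30% to 60% would be found in 81% of trials, and the documents do not say which rates apply. A reader might also infer that the plan will treat non-significance as proof that toxicity is not increased. It does not say so. The toxicity statement is a hypothesis in the rationale, worded with *may* and tied to animal studies, and no margin or decision rule turns p>0.05 into a safety claim. Equally, nothing in the supplied text guards against that reading.

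**Conclusion.** The concern holds in limited form. In the supplied Amendment 2 synopsis, Fisher's exact test is the only inferential safety method, and no between-arm estimate or interval is stated. For toxicities with a doxorubicin rate below about 20%, the test is more likely than not to miss a doubling, by a wide margin at 10% or less, so non-significance there is uninformative. For common toxicities, at about 30% or more, a doubling would be found with at least 80% power.

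This rests on a two-sided 5% level, assumed event rates, a doubling as the effect, and all 105 subjects contributing; power falls if fewer are treated. It is a cheap improvement to how the only secondary objective is reported, and does not affect the efficacy analyses.

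**What to change.** Amend the Safety paragraph of Statistical Methods along these lines:

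*For each safety comparison, the number and percentage of subjects with at least one event will be given by arm, together with the risk difference (INNO-206 minus doxorubicin) and its two-sided 95% confidence interval (Miettinen-Nurminen or Newcombe; one to be chosen in advance). Fisher's exact p-values, if shown, are supportive only. Any statement that toxicity is not increased will cite the upper confidence limit and will not rest on p>0.05.*

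Counting subjects also settles a smaller point: the current sentence refers to a total number of AEs, which is an event count, whereas Fisher's test needs subjects with and without an event.

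The cost is a few sentences and one more column in the safety tables, with no change to sample size, conduct or data collection. Safety conclusions will look less definite, which is accurate for 70 versus 35 subjects.
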